**SUMMARY OF CHANGES**

**PRIMARY REASON(S) FOR THIS AMENDMENT:**

Section Number (s)	Section Title(s)	Description of Change (s)	Rationale
1.0 2.1 6.0 7.1.5.3.2 7.2	Trial Summary Trial Design Flow chart Safety Follow-up Visit Assessing and Recording Adverse Events	The protocol collection period for AEs was revised to 90 days after treatment discontinuation, 30 days if the subject initiates new anticancer therapy less than 30 days after study treatment discontinuation, or the day new anticancer therapy is initiated if between 30 days and 90 days after study treatment discontinuation.	This change was made at the request of the FDA to allow late toxicities that can be observed with immunomodulatory agents to be collected.
2.1 2.2 4.2.2 5.2 Trial Treatment(s)	Trial Design Trial Diagram Rationale for Dose Selection/Regimen	The starting dose has been changed from 10 mg BID to 25 mg BID. A 10 mg BID (DL-1) dose is added as an alternative dose should 25 mg BID prove to be intolerable	This change was made at the request of the FDA to ensure the dose escalation from DL1 to DL2 does not exceed 2 fold.
5.1.2	Subject Inclusion Criteria	Subjects to be enrolled to the study are defined as refractory to or intolerant of existing therapy(ies) known to provide clinical benefit for their condition.	This change was made at the request of the FDA to ensure patients to be enrolled in this trial are those who have exhausted all current approved therapeutic options.
5.1.3	Subject Exclusion Criteria	Examples of A2a receptor antagonists CPI-444, HTL1071, PBF-509 are added to exclusion criteria # 3.	This change was made at the request of the FDA to clarify A2a receptor antagonists that preclude trial inclusion.

Section Number (s)	Section Title(s)	Description of Change (s)	Rationale
5.2.2.1	Replacement of Subjects in DLT period	The protocol was clarified to better describe the situation when patients are experiencing DLT but allowed to remain in the trial. Language is added to define “the subject is deriving clinical benefit upon resolution of the DLT to a $\leq$ Grade 1 adverse event and after discussion with the sponsor.”	This change was made at the request of the FDA as an extra safety precaution.
5.2.3	Guideline for Dose Modification and Treatment Discontinuation”	The protocol was clarified the section is applicable to both part 1 and part 2.	This change was made at the request of the FDA for clarification.
6.1	Flow Chart	Vital sign measurements were added to cycle 1 day 8 visit for both preladenant monotherapy arm and in combination with pembrolizumab arm.	This change was made at the request of the FDA as an extra safety precaution.
5.1.2	Subject Inclusion Criteria (Table 2)	The protocol was clarified in Coagulation section for INR and PT values when patients are using anticoagulant therapy.	This change was made at the request of FDA for clarification.
5.2.3.2	Table 8	Delete language “Appropriate resuscitation equipment should be available in the room and a physician readily available during the period of drug administration.” Since it is no longer applicable in current study.	The language is not applicable in this study.

Section Number (s)	Section Title(s)	Description of Change (s)	Rationale
5.2.2	Definition of Dose-Limiting Toxicities	The duration of any Grade 3 or Grade 4 non-hematologic laboratory value was changed from 1 week to 72 hours.	This change was made at the request of the FDA as an extra safety precaution.
5.2.2	Definition of Dose-Limiting Toxicities	Liver function test was eliminated from the exceptions for any Grade 3 or Grade 4 non-hematologic laboratory value.	This change was made at the request of the FDA as an extra safety precaution.
5.2.2	Definition of Dose-Limiting Toxicities	Liver test abnormalities (Hy's Law) was added to the definition of DLT.	This change was made at the request of the FDA as an extra safety precaution.
5.5.2.2	Prohibited Concomitant Medications for Pembrolizumab	Protocol was clarified for glucocorticoids dose limit and conditions for pembrolizumab prohibited medication.	This change was made at the request of FDA for clarification.

**ADDITIONAL CHANGE(S) FOR THIS AMENDMENT:**

No additional changes.

**1.0 TRIAL SUMMARY**

Abbreviated Title	PhIb/II Study of Preladenant +/- Pembrolizumab in Subjects with Solid Tumor
Sponsor Product Identifiers	Preladenant (MK-3814) and pembrolizumab (MK-3475)
Trial Phase	Phase Ib/II
Clinical Indication	Treatment of Advanced Solid Tumors
Trial Type	Interventional
Type of control	No treatment control
Route of administration	Oral (preladenant) and intravenous (pembrolizumab)
Trial Blinding	Unblinded Open-label
Treatment Groups	
During Part 1 (dose escalation and confirmation phase) subjects will be allocated to one of two treatment arms:                      Arm 1: preladenant in monotherapy                      Arm 2: preladenant in combination with pembrolizumab
 
During Part 2 (expansion phase) subjects will be allocated to Arm 2 (preladenant in combination with pembrolizumab) in 2 select tumor cohorts.

Number of trial subjects	Approximately 100-120 subjects will be enrolled.
Estimated duration of trial	The Sponsor estimates that the trial will require approximately 42 months from the time the first subject signs the informed consent until the last subject's last study-related phone call or visit.
Duration of Participation	
Each subject will participate in the trial for up to 28 months from the time the subject signs the informed consent form (ICF) through the final protocol-specified contact.
 
After a screening phase of up to 28 days, each subject will be receiving assigned treatment for up to 24 months. After treatment discontinuation, subjects will be monitored for adverse events (AEs) and serious adverse events (SAEs) for 90 days. Subjects who initiate new anticancer therapy less than 30 days after study treatment discontinuation will be monitored for AEs/SAEs for 30 days. Subjects who initiate new anticancer therapy between 30 days and 90 days after study treatment discontinuation will be monitored for AEs/SAEs until the day new anticancer therapy is initiated. Subjects will be treated until progressive disease, unacceptable toxicity, intercurrent illness that prevents further administration of treatment, investigator's decision to withdraw treatment, subject withdrawal of consent, pregnancy of the subject, noncompliance with trial treatment or procedure requirements, subject completes treatment, or administrative reasons requiring cessation of treatment, at which point they will be discontinued from the study. Upon disease progression, subjects in the monotherapy arm will be able to cross-over to the combination regimen.

Randomization Ratio	N/A

A list of abbreviations used in this document can be found in Section 12.6.

Preladenant will be used throughout the protocol to refer to MK-3814 as supplied by the Sponsor.

Pembrolizumab will be used throughout the protocol to refer to KEYTRUDA® or MK-3475 as supplied by the Sponsor.

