Subjects who discontinue preladenant in monotherapy (Arm 1) due to progressive disease may, at the investigator's discretion and after consultation with the Sponsor, cross-over to the combination treatment (Arm 2) (see Sections 4.2.3.1 and 4.2.3.2). It will be at the discretion of the investigator whether to continue a subject on study treatment until repeat imaging is obtained. Once they discontinue from any part of the study, subjects will be treated at the discretion of the physician.

After treatment discontinuation, subjects will be monitored for AEs and SAEs for 90 days. Subjects who initiate new anticancer therapy less than 30 days after study treatment discontinuation will be monitored for AEs/SAEs for 30 days. Subjects who initiate new anticancer therapy between 30 days and 90 days after study treatment discontinuation will be monitored for AEs/SAEs until the day new anticancer therapy is initiated.

Subjects with an ongoing AE of Grade >1 at the time of treatment discontinuation will be followed until resolution of the AE to Grade 0-1, until considered stable by the treating physician, or until beginning a new anti-cancer therapy, whichever occurs first.

Subjects who discontinue treatment for reasons other than confirmed progressive disease will have post-treatment follow-up for disease status (including imaging) until progressive disease, initiating a new anti-cancer therapy, discontinuing from the study participation, or becoming lost to follow-up.

[figure not shown]
After confirmed progressive disease each subject will be contacted by telephone every 12 weeks (84±7 days) for survival until subject discontinues from the study, becoming lost to follow-up, death, or end of the study, whichever occurs first.

The trial will be conducted in conformance with Good Clinical Practices (GCP).

Specific procedures to be performed during the trial, as well as their prescribed times and associated visit windows, are outlined in the Trial Flow Chart - Section 6.0. Details of each procedure are provided in Section 7.0 – Trial Procedures.

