
 
Any Grade 3 or 4 non-hematological toxicity (not including laboratory, unless clinically significant medical intervention is required to treat the subject, or the abnormality leads to hospitalization, or the abnormality persists for >1 week)
 
	Yes	Treatment may be restarted when AE resolves back to baseline or to Grade 1.	Decrease dose by one dose level.	If AE persists for 12 weeks without resolution following reduction in dose. Permanent discontinuation should be considered for any severe or life-threatening event

In case toxicity does not resolve to Grade 0-1 within 12 weeks after last treatment, preladenant should be discontinued after consultation with the Sponsor.

With Investigator and Sponsor agreement, subjects with a laboratory adverse event still at Grade 2 after 12 weeks may continue treatment in the trial only if asymptomatic and controlled.

After any Grade 4 drug-related adverse event, subjects should not restart study treatment without consultation with the Sponsor. (Toxicity must have resolved to 0-1 or baseline prior to restarting).

Dose reductions are not permitted during Cycle 1.

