## 6.0 TRIAL FLOW CHART

### 6.1 Flowchart

Preladenant in Monotherapy (Arm 1 ; Part 1)												
	Screening	Treatment Phase						Tumor Assessment	End of Treatment	Post-treatment Follow-Up Phase		
		Cycle 1			Cycle 2-4		Cycles 5 and all Subsequent Cycles	Every 9 weeks	Discontinuation	Safety Follow-up		Survival Follow-Up 
		Day 1	Day 8	Day 15	Day 1	Day 15	Day 1		At Treatment Discontinuation	30 days after the last dose	90 days after the last dose	Every 12 weeks post discontinuation
Scheduling Window (Days) 	-28 to -1	+3	±3	±3	±3	±3	±3	±7		+7	+7	±7
Administrative Procedures												
Informed Consent 	X											
Informed Consent for Optional Future Biomedical Research 	X											
Inclusion/Exclusion Criteria 	X											
Subject Identification Card 	X											
Medical History 	X											
Prior Oncology Treatment History 	X											
Prior Medications 	X											
Concomitant Medications 	X	X	X	X	X	X	X		X	X		
Clinic Procedures/Assessments												
Physical Examination 	X	X			X		X		X 	X		
12-Lead Electrocardiogram 	X											
Vital Signs 	X	X	X	X	X		X		X	X		
ECOG Performance Status 	X	X			X		X		X	X		
Dispense preladenant 		X			X		X					
Adverse Events Reporting 	X	X	X	X	X	X	X		X	X	X	

Preladenant in Monotherapy (Arm 1 ; Part 1)												
	Screening	Treatment Phase						Tumor Assessment	End of Treatment	Post-treatment Follow-Up Phase		
		Cycle 1			Cycle 2-4		Cycles 5 and all Subsequent Cycles	Every 9 weeks	Discontinuation	Safety Follow-up		Survival Follow-Up 
		Day 1	Day 8	Day 15	Day 1	Day 15	Day 1		At Treatment Discontinuation	30 days after the last dose	90 days after the last dose	Every 12 weeks post discontinuation
Scheduling Window (Days) 	-28 to -1	+3	±3	±3	±3	±3	±3	±7		+7	+7	±7
Tumor Imaging and RECIST 1.1 Response Assessment 	X							X	X			
Survival Status 												X
Laboratory Procedures/Assessments												
Archival or Newly Obtained Tumor Tissue Collection for Biomarker Analysis and Molecular Profiling 	X											
Blood for Genetic Analyses 		X										
Hematology 	X	X	X	X	X	X	X		X	X		
Blood for RNA Analyses 		X			X		X		X			

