4. Record medications taken 28 days prior to C1D1 and all medications taken up to and including 30 days after the last dose of study drug or the End-of-Treatment (whichever is later). Refer to Inclusion/Exclusion criteria for prohibited medications and washout periods.
5. Must be performed within 3 days prior to Day 1 of each cycle unless otherwise noted to coincide with the clinical and laboratory procedures. Physical examination, ECOG Performance Status, ECG, Vital Signs must be performed within 3 days prior to C1D1. It is not necessary to repeat C1D1 testing if the Screening testing was performed within 3 days prior to C1D1. Full Physical Examination will be performed at the Screening Visit and at the Treatment Discontinuation Visit. Directed Physical Examination will be done at all other visits.
6. Perform standard 12-lead ECG reporting ventricular rate, PR and QRS duration and QT/QTcF intervals prior to any blood collections or other study procedures.
7. Vital signs include blood pressure, pulse rate, and respiratory rate while sitting; temperature, height (at screening only), and weight.
8. After Cycle 1, preladenant may be dispensed up to 3 days prior to the cycle start to coincide with the physical exam. Study drug may only be dispensed after the treating physician has confirmed the subject will continue on to the next cycle. Each cycle is 21 days. Subjects may receive treatment for up to 35 cycles.

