9. Adverse events and serious adverse events will be recorded from the time of treatment allocation. All adverse events and serious adverse events that occur after the consent form is signed but before treatment allocation must be reported by the Investigator if they cause the subject to be excluded from the trial, or are the result of a protocol-specified intervention, including but not limited to washout or discontinuation of usual therapy or a study procedure. After treatment discontinuation, each subject will be followed for 90 days for adverse event and serious adverse event monitoring, 30 days if the subject initiates new anticancer therapy less than 30 days after study treatment discontinuation, or the day new anticancer therapy is initiated if between 30 days and 90 days after study treatment discontinuation. Subjects with an ongoing AE of Grade >1 at the time of treatment discontinuation will be followed until resolution of the AE to Grade 0-1, until considered stable by the treating physician, or until beginning a new anticancer therapy, whichever occurs first.
10. Baseline radiology images by CT (or MRI) of chest, abdomen, and pelvis, and all known tumor sites (if evaluable by imaging) must be obtained within 28 days prior to C1D1 and must be repeated every 9 weeks ( $\pm 7$  days) from C1D1 (See SIM). Imaging must be obtained at the End of Treatment visit at discontinuation unless done within the previous 4 weeks. Images are to be submitted to the central imaging vendor for potential future central analysis.
11. After confirmed disease progression subjects will be contacted by telephone every 12 weeks for survival until withdrawal of consent to participate in the study, becoming lost to follow-up, death, or end of the study, whichever occurs first.
12. Tumor tissue (archival or newly obtained biopsy) will be required at Screening upon signing the informed consent for the study. This sample will be assessed to collect information on biomarkers for all subjects enrolled in the study. Tumor tissue will be sent to central laboratory for biomarker analysis and leftover tissue may be saved for future biomedical research (FBR) if the subject signs the FBR consent.

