### **7.1.5.3 Post-Treatment Visits**

#### **7.1.5.3.1 End of Treatment – Discontinuation Visit**

The Discontinuation Visit should occur at the time study treatment is discontinued for any reason. If the Discontinuation Visit occurs 30 days from the last dose of study treatment, at the time of the mandatory Safety Follow up Visit, the Discontinuation visit procedures and any additional Safety Follow-up procedures should be performed. Visit requirements are outlined in Section 6.0- Trial Flow Chart. Additional details regarding subject withdrawal and discontinuation are presented in Section 5.7– Subject Withdrawal/Discontinuation.

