All adverse events that occur after the consent form is signed but before treatment allocation/randomization must be reported by the investigator if they cause the subject to be excluded from the trial, or are the result of a protocol-specified intervention, including but not limited to washout or discontinuation of usual therapy, diet, placebo treatment or a procedure. From the time of treatment allocation/randomization through 90 days following cessation of treatment, or 30 days following cessation of trial treatment if the subject initiates new anticancer therapy, whichever is earlier, all adverse events must be reported by the investigator. Such events will be recorded at each examination on the Adverse Event case report forms/worksheets. The reporting timeframe for adverse events meeting any serious criteria is described in section 7.2.3.1. The investigator will make every attempt to follow all subjects with non-serious adverse events for outcome.

Electronic reporting procedures can be found in the Electronic Data Capture (EDC) data entry guidelines. Paper reporting procedures can be found in the Investigator Trial File Binder (or equivalent).

Adverse events will not be collected for subjects during the pre-screening period (for determination of archival tissue status) as long as that subject has not undergone any protocol-specified procedure or intervention. If the subject requires a blood draw, fresh tumor biopsy etc., the subject is first required to provide consent to the main study and AEs will be captured according to guidelines for standard AE reporting.

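### The 90-day AE/SAE window runs from treatment discontinuation, but the safety contacts are scheduled from the last dose, so after a 12-week hold the last AE contact falls up to 84 days before the window ends

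*Combined protocol and SAP*

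**What the plan says.** **The collection rule.** Section 1.0 states: "After treatment discontinuation, subjects will be monitored for adverse events (AEs) and serious adverse events (SAEs) for 90 days". Section 2.1 repeats it: "After treatment discontinuation, subjects will be monitored for AEs and SAEs for 90 days". The Adverse Events Reporting row of the flow chart carries a footnote (9 for Arm 1, 10 for Arm 2 and cross-over subjects) with the same anchor: "After treatment discontinuation, each subject will be followed for 90 days for adverse event and serious adverse event monitoring". Section 7.1.5.3.2 says the same. Each of these also counts the 30-day and 90-day cut-offs for new anticancer therapy from treatment discontinuation.

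**The schedule.** In both flow charts the Safety Follow-up columns in which AE reporting is marked are headed 30 days and "90 days after the last dose", each with a +7-day window. Section 7.1.5.3.2 places the safety visit about 30 days after the last dose, one paragraph before it counts 90 days from discontinuation.

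**Other wording.** Sections 7.2 and 7.2.3.1 refer to cessation of treatment; 7.2 requires AE reporting "through 90 days following cessation of treatment". The term is not tied to either date.

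**The concern.** If the last dose and the discontinuation of treatment were always the same day, the two anchors would be interchangeable. The protocol shows that they are not. The affected subjects are also not a random subset: they are those whose drug was withheld for toxicity and never restarted.

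The 90-day period exists to catch late toxicity. The Summary of Changes gives that as its reason, Section 5.2.3.2 warns that immune-related events can appear months after treatment, and Section 2.1 says that late toxicities will inform the final RP2D. Section 8.6.2 then summarizes AEs by dose level and arm. If some sites make their last AE contact by the column heading and others by the footnote, late AE counts in these subjects will partly reflect site practice.

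**Working it through.** **1. Reproduce the plan's own figure.** Section 1.0 gives up to 28 months of participation. With a month of 365.25/12 = 30.4375 days:

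- 28 days + 24 months + 90 days = (28 + 730.5 + 90)/30.4375 = 27.9 months
- with 35 cycles of 21 days: (28 + 735 + 90)/30.4375 = 28.0 months

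The figure reproduces. It does not settle the anchor, because it assumes no gap between the last dose and the end of treatment.

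**2. Can the two dates differ?** Three places say so.

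- Flow-chart footnote 4 records medications "up to and including 30 days after the last dose of study drug or the End-of-Treatment (whichever is later". However it is parsed, it treats the two dates as different.
- Section 7.1.5.3.1 foresees a gap of 30 days: "If the Discontinuation Visit occurs 30 days from the last dose of study treatment, at the time of the mandatory Safety Follow up Visit".
- The Table 7 notes allow a long hold: "In case toxicity does not resolve to Grade 0-1 within 12 weeks after last treatment, preladenant should be discontinued". Table 8 has a comparable 12-week limit from the last pembrolizumab dose for several toxicities. Section 7.1.1.9 contemplates interruptions of 12 weeks or more after consultation, so 12 weeks is the rule-based limit and not a hard cap.

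**3. Size of the gap.** Let Day 0 be the last dose of any study drug and g the days from then to discontinuation.

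- Stated window ends on Day g + 90.
- Last scheduled AE contact is on Day 90, or Day 97 with the +7 window.
- Window without a scheduled AE contact: (g + 90) − 90 = g days, or (g + 90) − 97 = g − 7 days with the +7 window (none if g is 7 or less).
- Time from discontinuation to last AE contact: 90 − g, or 97 − g.

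| g (days) | Window ends | Last AE contact | Window without contact (days) | Discontinuation to last contact (days) |
|---|---|---|---|---|
| 0 | Day 90 | Day 90–97 | 0 | 90–97 |
| 21 | Day 111 | Day 90–97 | 14–21 | 69–76 |
| 42 | Day 132 | Day 90–97 | 35–42 | 48–55 |
| 63 | Day 153 | Day 90–97 | 56–63 | 27–34 |
| 84 | Day 174 | Day 90–97 | 77–84 | 6–13 |

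For an assumed longer hold of 98 days, the 90-day column date would fall 8 days before discontinuation (90 − 98 = −8).

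**4. New anticancer therapy.** With g = 84, suppose new therapy starts on Day 94. That is 94 − 84 = 10 days after discontinuation, so the stated rule collects for 30 days after discontinuation, to Day 84 + 30 = 114. Counted from the last dose, Day 94 already lies beyond 90 days.

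**5. Do other visits fill the gap?** In both flow charts the AE row is blank under Tumor Assessment and under Survival Follow-Up. A subject stopped for toxicity without progression is still imaged every 9 weeks, but AE collection is not scheduled there.

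**The case against.** The strongest reply is that the collection rule itself is consistent. Every sentence that uses the word discontinuation gives the same anchor, the AE row points to footnotes 9 and 10, and nothing in the text says that AE collection stops 90 days after the last dose. The column headings schedule contacts; they do not define the reporting period. This stands. A reader might infer that the plan contains two rival collection windows, with AE reporting closing on Day 90 under one of them. The documents do not support that. They support only a schedule that does not reach the end of the stated window.

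A reader might also take cessation of treatment as a third anchor. It reads naturally as discontinuation, and no different date follows from it. It merely lacks a definition.

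Two safeguards cover much of what matters in these subjects. An AE above Grade 1 that is ongoing at discontinuation is followed to resolution, stability or new anticancer therapy (Section 2.1 and footnotes 9 and 10), and related SAEs are reportable at any time (Section 7.2.3.1). Subjects on hold have not yet discontinued and remain on treatment-phase visits, so reading the 30-day visit as due on Day 30 of a hold would be strained.

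Finally, 84 days is a limiting case. In Arm 2 it requires both drugs to be held, since Section 5.2.3.1 lets one continue, and the documents give no frequency for such holds. All of this narrows the point. It does not give a site that follows the footnote any scheduled AE contact between Day 97 and Day 174.

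**Conclusion.** The point holds as a mismatch between the stated collection window and the contacts planned to serve it. The shortfall equals the time from the last dose of any study drug to discontinuation: zero for a subject who stops without a hold, and 84 days (77 if the full visit window is used) at the 12-week limit. In that case the last AE contact comes only 6 to 13 days after discontinuation.

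What is exposed is new-onset non-serious AEs, related or not, and SAEs judged unrelated. It would be wrong to infer from the primary safety objective that the primary endpoint is at risk: the DLT rate is observed in Cycle 1 and is untouched, as is the sample size. The conclusion assumes that sites make contacts as the column headings say and that all study drug was on hold. How many subjects this concerns cannot be derived from the documents, but it should be few. The correction is worth making because it is cheap and the shortfall falls on subjects stopped for toxicity.

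**What to change.** Define one anchor and use it throughout. The choice is the sponsor's. The least change follows footnotes 9 and 10:

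- Re-head the 30-day and 90-day Safety Follow-up columns in both flow charts to count from treatment discontinuation.
- Time the safety visit in Section 7.1.5.3.2 from the same date, and adjust the combined-visit sentence in Section 7.1.5.3.1 to match.
- State in Sections 7.2 and 7.2.3.1 that cessation of treatment means that date, including for the 30-day new-anticancer-therapy test.

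Sections 1.0 and 2.1 and footnotes 9 and 10 need no change. Footnote 4 should not be used as the model. Its wording can mean either 30 days after the later date, or the later of End-of-Treatment and 30 days after the last dose, and Sections 5.5.1 and 7.1.1.6.2 set the concomitant-medication period from the last dose alone.

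The cost is four column headings, a few sentences, and some extra weeks of AE contact for the few subjects stopped after a hold. Subjects who stop without a hold see no change.
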